Research question and objectives:	
Research Questions:
 
1. What are the characteristics of patients with NRG1 gene fusion-positive solid tumors treated with afatinib, and what are the characteristics of those treated with another systemic therapy? 
Study Objectives:
 
1. To describe the demographic and clinical characteristics of patients with NRG1 gene fusion-positive solid tumors treated with afatinib and of patients with NRG1 gene fusion-positive solid tumors treated with other systemic therapy.2. To calculate the ORR and DOR among patients with NRG1 gene fusion-positive solid tumors treated with afatinib and among patients with NRG1 gene fusion-positive solid tumors treated with other systemic therapy3. To estimate PFS (and TOT, TTP) among patients with NRG1 gene fusion-positive solid tumors treated with afatinib and among patients with NRG1 gene fusions treated with other systemic therapy4. To estimate OS among patients with NRG1 gene fusion-positive solid tumors treated with afatinib and among patients with NRG1 gene fusion-positive solid tumors treated with other systemic therapy5. To describe the incidence and severity of adverse events (AEs) among patients with NRG1 gene fusion-positive solid tumors while on treatment with afatinib or other systemic therapy
Study design:	This retrospective cohort study will be conducted via a multi-site medical chart review of patients with NRG1 gene fusion-positive solid tumors. Two cohorts of patients will be identified: the first includes any patient with NRG1 gene fusion-positive solid tumors who has received afatinib in any line of therapy (afatinib cohort). The second includes any patient with NRG1 gene fusion-positive solid tumors who has not received afatinib in any line of therapy (other systemic therapy cohort). All patients must have initiated treatment after 01/01/2017 and before 03/31/2020. To remove potential bias, patients who died prior to 3 months following treatment initiation are still eligible. Data collection is anticipated to occur in Q3/Q4 of 2020, allowing for a minimum follow-up of approximately 3 months. Demographics, clinical characteristics, safety, and clinical outcomes (ORR, DOR, DOCB, TOT, TTP, PFS, OS, and AEs will be described for both patient cohorts.

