9. RESEARCH METHODS

9.1 STUDY DESIGN

This is a non-interventional, retrospective, US, multi-site, cohort study based on existing data from medical records of patients with *NRG1* gene fusion-positive solid tumors treated with afatinib or other systemic therapy. Two cohorts of patients will be identified. The first includes any patient with *NRG1* gene fusion-positive solid tumors who has received afatinib in any line of therapy (afatinib cohort) between 01/01/2017 and 03/31/2020. The second includes any patient with *NRG1* gene fusion-positive solid tumors who has not received afatinib in any line of therapy (other systemic therapy cohort) during the same period and no history of afatinib use. Follow-up will include at least 3 months after initiation of afatinib or other systemic therapy, unless a patient died prior to 3 months of follow-up.

In total, up to 120 patients with *NRG1* gene fusion-positive solid tumors will be selected for this study, of whom up to 70 will be afatinib-treated and up to 50 will be treated with other systemic therapy. Study objectives are to describe these patients and calculate the ORR in each group, as well as to estimate PFS, TOT, TTP, OS, DOR, and DOCB along with describing the incidence and severity of AEs among patients in the two cohorts. Data to be collect through this medical chart review include patient demographics, clinical characteristics at the time of diagnosis/initiation of a line of therapy, treatment-related data points (dates of initiation, discontinuation, dosing), AEs occurring during therapy, disease response, date of progression and/or death.

Given the small number of patients targeted for study inclusion and anticipated differences in baseline characteristics between afatinib-treated and patients treated with other systemic therapies, statistical comparisons are not planned. In lieu of statistical comparisons between cohorts, the non-afatinib arm will provide context for interpreting results among those treated with afatinib. Specifically, this context includes what patients with *NRG1* gene fusions not treated with afatinib look like, how they are managed and treated, and what their clinical outcomes look like. The non-afatinib arm will provide a broader understanding of *NRG1* gene fusions among patients with solid tumors

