Data collection is anticipated to begin in the third/fourth quarter of 2020, allowing for a minimum follow-up period of 3 months. All patients are required to have initiated index therapy (i.e., afatinib in any line; other systemic therapy among those without any history of afatinib) between 01/01/2017 and 03/31/2020. As such, the maximum follow-up period is approximately 39 months. The index date is the date of initiation of afatinib or other systemic therapy between 01/01/2017 and 03/31/2020 for the other systemic therapy cohort.

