9.2.1 Provider/Site/Patient Selection

Provider Eligibility

Providers who meet the following criteria will be eligible to participate:

- 1) Are board-certified oncologist/hematologist.
- 2) Have treated/are treating at least one eligible patient with an *NRG1* fusion-positive solid tumor.
- 3) Are able to participate in research approved by an external institutional review board (IRB).
- 4) Agree to participate in data quality assurance/control processes.

Providers will select patients meeting the study eligibility criteria as described below. Providers will be asked to select eligible patients chronologically, starting with the first patient who first initiated any line of afatinib or chemotherapy, on or after 01/01/2017 through 03/31/2020.

Patient Eligibility

Inclusion Criteria:

- Adults, 18 years of age or older, at the time of diagnosis with any solid tumor.
- Confirmed *NRG1* gene fusion in any solid tumor.
- Initiated afatinib or other systemic therapy (in any line of therapy) for treatment of a solid tumor with *NRG1* gene fusion on or after 01/01/2017 through 03/31/2020.

- Followed up for ≥ 3 months after initiation of afatinib or other systemic therapy (unless deceased prior to 3 months of follow-up).

Exclusion Criteria:

- Treatment with any TKI/ErbB-directed therapy other than afatinib

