The ORR among patients with *NRG1* gene fusion-positive solid tumors treated with afatinib and among patients with *NRG1* gene fusion-positive solid tumors treated with other systemic therapy will be calculated as the proportion of patients with a complete response (CR) or partial response (PR) out of all patients (CR+PR/all patients) (see **Table 2** below). Disease response for determining the ORR will be reported as recorded in the patient's EHR, including the date of radiographic imaging used to substantiate the patient's initial and best response to therapy. Providers will indicate whether the patient experienced a CR, PR, stable disease (SD), or progressive disease (PD). No independent blinded review of radiology studies will be conducted. Lesion measurements at baseline (initiation of afatinib; initiation of other systemic therapy for non-afatinib treated patients), initial response, and best response will be abstracted as available. Changes in the number, locations, and sizes of lesions at initial and best response to therapy will be evaluated by [REDACTED] using RECIST v1.1 guidelines. The sum of lesion measurements will be assessed at baseline and at follow-up scans to calculate the percent change in sum of target lesions, as well as account for new lesions on follow-up scan in order to classify response by RECIST v1.1 criteria. Actual scan images will not be reviewed; the calculation of real-world disease response will be based on the lesion measurements provided. Other outcomes include PFS, TOT, TTP, OS, DOR, DOCB, AEs. Definitions of these outcomes are shown in **Table 2**.

Table 2. Study outcomes and definitions.

Outcome	Definition
ORR	Proportion of patients with a complete response (CR) or partial response (PR) out of all patients (CR+PR/all patients) at initial response assessment and best response
DOCB	Duration of clinical benefit (DOCB) will be calculated as the time from initial response (for any patient with a complete, partial, or stable disease response initially) until the earliest of either disease progression or death. Patients who discontinue therapy due to a reason other than progression will be censored on the date of discontinuation. Patients still on therapy at the time of data cut-off will be censored on their last visit date.

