9.7 DATA ANALYSIS

Demographic and clinical characteristics will be reported by descriptive analyses including counts and frequencies for dichotomous and categorical variables, while measures of centrality (mean, median) and spread (min, max, standard deviation, interquartile range, as appropriate) will be used for continuous variables. These characteristics will be described at the time of initial diagnosis of advanced/metastatic disease and at the time of initiation of each line of therapy received, for the afatinib cohort and separately for the other systemic therapy cohort. No statistical comparisons will be made across these two cohorts in terms of demographic, clinical characteristics, and clinical outcomes.

The calculations for all outcomes (e.g., ORR, DOR, DOCB, TOT, TTP, PFS, OS) are defined in **Table 2** in Section **9.3.2 Outcomes**. For disease response, the point estimate for ORR and associated 95% confidence interval (CI) will be calculated for initial response to index therapy (i.e., afatinib or other systemic therapy) and best response to index therapy, for each cohort. ORR will be reported among subgroups within each of the treatment cohorts, by tumor type and line of therapy. The Kaplan-Meier method will be used to estimate time-to-event outcomes (DOR, DOCB, TOT, TTP, PFS, and OS) to account for any right-censoring (e.g., patient had not discontinued therapy, patient had not progressed, or died). Time-to-event outcomes will be described for each of the two treatment cohorts and in subgroups within the two treatment cohorts, according to solid tumor and line of therapy. All study outcomes will be reported separately for those treated with afatinib monotherapy. In the event an outcome cannot be assessed for a given patient, that patient would be omitted from assessment of that outcome; reason for omission in a given outcome assessment will be reported.

Cumulative incidence, severity, and timing of AEs during the index therapy will be summarized and displayed in number/percentage form for each of the treatment cohorts, separately. All safety endpoints will be analyzed descriptively. AE reporting is summarized in Section **11 Management and Reporting of Adverse Events/Adverse Reactions**.

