9.9 LIMITATIONS OF THE RESEARCH METHODS

The limitations of this approach include provider selection bias, patient selection bias, and the lack of source document verification. Regarding bias, only providers who meet the study eligibility requirements and who volunteer to participate in the research study are known; therefore, the representativeness of the providers to all oncologists in the U.S. cannot be verified directly. Additionally, providers will select the patients meeting study eligibility criteria, so they may not include all potentially eligible patients. As such, the representativeness of the patient sample to all patients in the U.S. or in the population of patients within the [REDACTED] also cannot be verified. Source document verification cannot be performed by [REDACTED] however, quality assessment/control procedures to minimize misclassification errors are described in **Section 9.8 – Quality Control**.

- 1) As an exploratory, retrospective, non-randomized study with up to 70 and up to 50 patients per cohort (respectively), post-hoc propensity score matching cannot be conducted and unadjusted/crude comparisons between the two cohorts cannot be made as underlying demographic/clinical characteristics may exist between the cohort. Therefore, statistical comparisons of outcomes between the two cohorts cannot be made.
- 2) Not all patient characteristics will be included in the data collection (e.g., income and other variables that may influence provider-prescribing behavior or treatment decisions) and cannot be accounted for in the descriptive analyses.
- 3) Loss to follow-up during the study period may occur if patients transfer care to other providers and centers. As such, treatments, visits, and outcomes occurring after the date of last visit may be missing.
- 4) Treatment patterns reflected in the study represent only the practices of providers who have agreed to participate, and may vary from non-responding providers, i.e., those who refused study participation or who were unresponsive to the screening invitation. No data is available to describe non-responders.
- 5) This study employs purposive sampling that selects providers and patients based on pre-specified selection criteria and hence this may not be representative of all patients diagnosed with *NRG1* gene fusion-positive solid tumors treated with the drugs of interest or representative of all providers treating these types of patients.

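### The 3-month follow-up criterion keeps early deaths but drops living patients who lose contact early, so inclusion depends on events after index and early survival and ORR can be biased

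*Combined protocol and SAP*

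**What the plan says.** The inclusion criteria in Section 9.2.1, and the Population row of the abstract (Section 4), ask for 3 or more months of follow-up "after initiation of afatinib or other systemic therapy (unless deceased prior to 3 months of follow-up". Section 9.1 repeats the rule: "Follow-up will include at least 3 months after initiation of afatinib or other systemic therapy, unless a patient died prior to 3 months of follow-up". The abstract gives the reason for the exception: "To remove potential bias, patients who died prior to 3 months following treatment initiation are still eligible".

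Section 9.1 places index therapy between 01/01/2017 and 03/31/2020 and data collection in the third or fourth quarter of 2020, "allowing for a minimum follow-up period of 3 months".

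Four other places bear on the point.

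- Section 9.9, limitation 3, expects some attrition: "Loss to follow-up during the study period may occur if patients transfer care to other providers and centers". It treats the consequence as missing later data only.
- Section 9.12 checks selection by comparing the number of patients who meet the criteria with the number submitted.
- Table 2 (Section 9.3.2) defines ORR as responders "out of all patients (CR+PR/all patients) at initial response assessment and best response", while Section 9.7 says: "In the event an outcome cannot be assessed for a given patient, that patient would be omitted from assessment of that outcome".
- Table 2 starts OS at the first therapy in the metastatic setting and censors living patients when last seen. Section 9.7 names Kaplan-Meier for all time-to-event outcomes.

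**The concern.** The criterion concerns actual follow-up. A waiver for death would be unnecessary if only potential follow-up were meant. Whether a patient enters the study then depends on what happened after index. The death waiver rightly avoids a cohort made up only of 3-month survivors, but it deals with one half of the selection and leaves the other half in place.

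No comparison between cohorts is planned, so the absolute ORR and time-to-event estimates are the result, and Section 7 says they may support label-expansion requests. With up to 70 and up to 50 patients, a few uncounted exclusions can move them. The selection check in Section 9.12 cannot show this, because it counts only patients who already qualify. Section 9.7 describes no sensitivity analysis for it.

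**Working it through.** **1. The plan's own figure.** From the last index date, 31 March 2020, to the first day of Q3, 1 July 2020, is 92 days, or 3.0 months. The stated 3-month minimum reproduces. Everyone already has that much potential follow-up.

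**2. Who is removed.**

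| Status at month 3 | Included? |
|---|---|
| Died before month 3 | Yes, by the waiver |
| Known alive at month 3 | Yes |
| Alive when last seen, before month 3 | No |

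Only the third row is affected. Stopping therapy does not matter in itself: a patient who stops at week 4 and is still seen at month 3 qualifies.

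**3. Direction for survival.** Each Kaplan-Meier factor is 1 - d/n. Dropping a patient who would have been censored leaves d unchanged and lowers n at every event time before that patient's last contact. Each factor falls or stays the same, so the estimate cannot rise.

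**4. Size for survival from index.** Assume a constant death hazard a, a constant and independent loss hazard b, and time in months. Loss is expressed as 1 - exp(-3b), the probability of loss in the absence of death. Among included patients:

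- s = exp(-3(a+b)), known alive at month 3
- d = [a/(a+b)] × (1 - s), died under observation
- reported 3-month survival = s/(s+d)

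For true survival of 85% and loss of 10%: s = 0.85 × 0.90 = 0.765; a/(a+b) = 0.1625/(0.1625 + 0.1054) = 0.607; d = 0.607 × 0.235 = 0.1426; s/(s+d) = 0.765/0.9076 = 84.3%, a shift of -0.7 points. The share excluded is 1 - 0.9076 = 9.2%.

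| True 3-month survival | Loss 3% | Loss 10% | Loss 20% |
|---|---|---|---|
| 95% | 94.9% | 94.7% | 94.4% |
| 85% | 84.8% | 84.3% | 83.5% |
| 75% | 74.7% | 73.9% | 72.7% |

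The shifts run from about -0.1 to -2.3 points. In 4,000 simulated data sets of 77 patients (true survival 85%, loss 10%), the mean estimate was 85.0% with early leavers censored and 84.3% with them dropped. It was never higher when they were dropped.

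**5. If loss is informative.** Take 100 patients: 15 recorded early deaths, 10 lost alive, 75 known alive at month 3. The criterion gives 75/90 = 83.3%. The truth is 85% if none of the 10 died by month 3 (bias -1.7 points), 80% if half did (+3.3) and 75% if all did (+8.3).

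**6. ORR.** Let R be the true ORR over all treated patients, L the share lost alive before month 3, and r their response rate. Reported ORR = (R - L × r)/(1 - L). This exceeds R when r is below R and falls short of R when r is above it. Assume R = 30% and early deaths (share D) counted as non-responders, so that 3-month survivors respond at R/(1 - D) on average.

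- No lost patient responded: L = 3%, 5%, 10%, 15% gives 0.30/(1 - L) = 30.9%, 31.6%, 33.3%, 35.3%.
- D = 15%, L = 10%, lost patients respond like other 3-month survivors (0.30/0.85 = 35.3%): (0.30 - 0.0353)/0.90 = 29.4%. At half that rate: 31.4%.
- D = 25%, L = 15%, same rate as other survivors (0.30/0.75 = 40%): (0.30 - 0.06)/0.85 = 28.2%.

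Over D of 5% to 25% and L of 3% to 15%, the shift is -1.8 to +5.3 points.

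**7. Scale.** The 95% half-width at n = 70 and 30% is 1.96 × √(0.30 × 0.70/70) = 10.7 points, as in Table 4, where it is labelled SE.

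**The case against.** A reader might infer that the plan's ORR and early survival are biased, with ORR too high and survival too low. The documents do not support that much.

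- **No loss rate is given.** Section 9.9 says only that loss may occur. With no early leavers there is no bias.
- **The ORR sign is not fixed.** The only reason for loss named in Section 9.9 is transfer of care, which does not show that leavers are non-responders. The +5.3 end of the range assumes that none of them responded.
- **ORR depends on two conflicting rules.** Under the omission rule in Section 9.7, a patient lost before any response assessment leaves the ORR even without this criterion. The criterion adds an ORR effect only under Table 2's full denominator, or for patients assessed before loss.
- **OS has a different time origin.** It starts at first metastatic therapy, so the survival figures above apply to OS only where index is the first metastatic line. For later-line patients the effect falls later on the OS curve.
- **The downward direction is for patients who would be censored.** A patient who progressed and then left care alive is an event for PFS, and dropping that patient raises the PFS estimate.
- **The shifts are smaller than the sampling error at n = 70.**

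All of this stands. It limits what can be said about sign and size. It does not touch the asymmetry itself, which is plain in the text, is not counted anywhere and has no offsetting benefit. A shift that more patients would not remove is not excused by a wide interval.

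**Conclusion.** The criterion selects on events after index. It keeps early deaths, drops living patients whose contact ended before month 3, and does no work that the calendar window does not already do. Compared with censoring these patients, it lowers early Kaplan-Meier survival or leaves it unchanged. Under independent loss of 3% to 20% and true 3-month survival of 75% to 95%, the shift is about 0.1 to 2.3 points from index. Against the truth, informative loss can reverse the sign. ORR can shift by about -1.8 to +5.3 points at a true ORR of 30% and loss of 3% to 15%, upward if those lost respond less often than included patients. Every loss, death and response rate here is an assumption. The defensible statement is that the estimates can be biased by an amount the plan has no means of showing, and that this should be corrected before the protocol is finalized.

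**What to change.** 1. In the abstract, Section 9.1 and Section 9.2.1, replace the actual-follow-up requirement with potential follow-up: index therapy started on or before 03/31/2020 and abstraction at least 3 months after index.
2. Include patients lost alive before 3 months and censor them under each outcome's own Table 2 rule. These rules differ: OS uses the date last seen, TOT and TTP the last treatment date, and DOR and DOCB the discontinuation date for patients who stop for a reason other than progression.
3. Add the missing PFS censoring date for a living patient who stops therapy without progression. Table 2 does not give one, and some of the added patients will need it.
4. Reconcile the ORR denominator in Table 2 with the omission rule in Section 9.7 by keeping unassessed patients as non-responders in the main ORR. Changing the criterion alone would not settle ORR.
5. Report the number of early leavers per cohort, and ORR with and without them.

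The cost is an edit to the eligibility text in three places, the eCRF screener, one PFS censoring rule and one sentence in Section 9.7. The milestones place protocol finalization (July 2020) ahead of or at the start of data collection (Q3/Q4 2020). The downside is that a few patients with sparse data enter and ORR may be slightly lower.

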9.3 VARIABLES

9.3.1 Exposures

The primary exposure of interest is treatment with afatinib. Two cohorts of patients will be created: the afatinib-treated cohort includes patients with an *NRG1* gene fusion-positive solid tumor who had received afatinib in any line of therapy; the second cohort includes patients with an *NRG1* gene fusion-positive solid tumor who had not received afatinib prior to the date of data collection. Patients treated with afatinib monotherapy and their outcomes will be described in addition to the two main aforementioned treatment groups.

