DOR	Duration of response will be calculated as the time from initial response (for any patient with a complete or partial response initially) until the earliest of either disease progression or death. Patients who discontinue therapy due to a reason other than progression will be censored on the date of discontinuation. Patients still on therapy at the time of data cut-off will be censored on their last visit date.
TOT	Time from initiation of a line of therapy until discontinuation for any reason; patients on therapy at the time of data cut-off will be censored on the last date of treatment.
TTP	Time from initiation of a line of therapy until discontinuation due to disease progression; patients on therapy or those who discontinued due to a reason other than disease progression will be censored on the last date of treatment.

PFS	Time from initiation of a line of therapy until disease progression or death; patients on therapy at the time of data cut-off will be censored on the last date of treatment. Patients who discontinue a line of therapy for a reason other than disease progression but who subsequently die prior to the receipt of any other therapy will be considered an event on the date of death.
OS	Time from initiation of any therapy in the metastatic setting until death; patients alive at the time of data cut-off will be censored on the last date the patient was seen by the provider/clinic.
AE	An adverse event is defined as any untoward medical occurrence in a patient administered a medicinal product and which does not necessarily have a causal relationship with this treatment. AEs from a prepopulated list (including “other, please specify”) during each line of therapy will be indicated by providers. The number and proportion of patients experiencing each AE reported during afatinib or other systemic therapy will be reported. See Section 11.1 and Table 3 for further details.

In addition to TOT, to further characterize treatment patterns for those treated with afatinib and those treated with other systemic therapy, the following will be collected (and calculated based on the collected data):

- Treatment history (i.e., regimens, duration, number of cycles, sequence)
- Starting dose of afatinib or other systemic therapy
- Dose modifications of afatinib or other systemic therapy (i.e., dose reductions and their timing, dose increases and their timing, dose delays and their duration and timing)

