9.4 DATA SOURCES

All study data will be entered by the investigators into the eCRF. The eCRF captures data for each of the study variables described in **Section 9.3 - Variables**. The eCRF is designed to allow providers to efficiently move through the patient chart or EMR based on the journey of the patient through the course of disease. The eCRF conforms to the rules and regulations of the Health Insurance Portability and Accountability Act (HIPAA) of 1996 governing the abstraction and storage of protected health information (PHI).

De-identified, patient-level data will be obtained from providers in the [REDACTED] [REDACTED] who will complete an electronic case report form (eCRF) for eligible patients. [REDACTED]

[REDACTED] will recruit providers from [REDACTED] to participate. [REDACTED] is a community of over 7,000 oncologists, hematologists and urologists from across the U.S., with varying levels of time in practice, from practices both within and outside of group purchasing organizations. A subset of this group (~800) participates in retrospective observational research studies. All provider participation in the study is voluntary.

To be eligible to participate, providers must have treated at least one patient meeting the study eligibility criteria, be able to participate in research approved by an external institutional review board (IRB), and agree to participate in data quality control processes. No provider at practices that require local IRB approval at the practice will be eligible to participate. A waiver of obtaining patient consent will be sought for the study. No protected health information (PHI) beyond dates of diagnosis, treatments, and outcomes will be collected.

Providers will abstract demographic-, clinical-, and treatment- related data as available from the patient's electronic health record (EHR), starting from the time of primary malignancy diagnosis through the last date of follow-up with the patient or death. Providers will complete an eCRF for all eligible patients and will begin data abstraction beginning with the first eligible patients and select consecutive patients moving forward in time. Data elements that are required are specified in the study inclusion/exclusion criteria; non-required data elements may be missing/unknown. Providers may abstract data into the eCRF for both patients they personally managed/treated or those managed/treated by other providers within their practice.

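### The TKI/ErbB exclusion has no time limit, so read literally it makes eligibility depend on treatment after the index line and can bias ORR, PFS and OS by an unknown amount

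*Combined protocol and SAP*

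**What the plan says.** The protocol has one exclusion criterion: "Treatment with any TKI/ErbB-directed therapy other than afatinib". It stands in section 9.2.1 and, in the same words, in the Abstract under Population. Neither place says whether it means treatment before, during or after the index therapy.

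Section 9.1 anchors entry to the index line: "All patients are required to have initiated index therapy" between 01/01/2017 and 03/31/2020. The chart visible to the provider runs well past that date. Section 9.4 has data abstracted from diagnosis "through the last date of follow-up with the patient or death", section 9.1 states that "the maximum follow-up period is approximately 39 months", and section 9.3.2 collects the regimens and their order.

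The outcomes affected are defined in section 9.3.2, Table 2. ORR is the "proportion of patients with a complete response (CR) or partial response (PR) out of all patients", so a patient who is excluded leaves both numerator and denominator. PFS is "Time from initiation of a line of therapy until disease progression or death". OS runs from the start of any therapy in the metastatic setting to death.

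**The concern.** Patients who receive another TKI or ErbB-directed agent after the index line are not a random subset. They came off the index therapy, often because it failed, and they lived long enough to start something else. If the criterion removes them, entry to the cohort depends on what happened after the index date. Response, progression and survival are then estimated in a group selected partly on those same outcomes.

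The study's own checks would not show this. Section 9.12 compares the patients submitted with the patients who meet the criteria; someone excluded for a later drug is in neither count. Section 9.8.2 reports only records corrected or dropped in data validation. The limitations in section 9.9 do not mention the issue, and section 9.12 treats the strictness of the criteria as a protection against selection bias. The Abstract deliberately keeps patients who die within 3 months, to avoid bias. Removing patients for what they received later works against that aim.

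The sponsor says that the data may support label-expansion requests (Abstract; section 7), so a selection effect in the single-cohort estimates matters even though the cohorts are not formally compared.

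**Working it through.** **Is a time limit given anywhere?** The criterion appears twice, both times without one. The index window in section 9.1 limits the start of index therapy, not the exclusion. Because the chart extends to last follow-up or death and the treatment sequence is recorded, a later agent is visible when eligibility is judged. The second cohort has a related feature by definition: it consists of patients "who had not received afatinib prior to the date of data collection".

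**The plan's precision figure.** Section 9.5, Table 4, gives ±10.7% for a proportion of 30% at n=70. This is reproduced by 1.96 × √(0.30 × 0.70 / 70) = 1.96 × 0.0548 = 0.107. It is a 95% half-width, although the table labels it SE.

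**Effect on ORR.** Let p be the true ORR, and let qR and qN be the shares of responders and non-responders removed for a later agent. Then

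ORR reported = p(1 − qR) / [p(1 − qR) + (1 − p)(1 − qN)].

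The documents give none of these three inputs. With p = 30% assumed:

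| qN | qR | Calculation | ORR reported | Shift (points) | Patients lost |
|---|---|---|---|---|---|
| 10% | 5% | 0.285 / (0.285 + 0.630) | 31.1% | +1.1 | 8.5% |
| 20% | 5% | 0.285 / (0.285 + 0.560) | 33.7% | +3.7 | 15.5% |
| 30% | 5% | 0.285 / (0.285 + 0.490) | 36.8% | +6.8 | 22.5% |
| 30% | 20% | 0.240 / (0.240 + 0.490) | 32.9% | +2.9 | 27.0% |
| 30% | 30% | 0.210 / (0.210 + 0.490) | 30.0% | 0 | 30.0% |
| 20% | 30% | 0.210 / (0.210 + 0.560) | 27.3% | −2.7 | 23.0% |

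The sign depends only on whether qN is larger than qR.

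**Effect with time built in.** A simulation gives qR and qN from a disease course instead of fixing them. All inputs are assumptions:

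- true ORR 30% or 40%;
- median time to progression 12 months in responders and 3 in non-responders;
- median time to death without progression 30 months;
- median survival after progression 8 months;
- a later agent starting 1.5 months after progression in 10%, 25% or 40% of those still alive;
- follow-up of 5 to 45 months.

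Results under the literal rule, compared with keeping everyone:

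- 6.5% to 27.3% of patients are removed. In the highest 30%-ORR case, 30.6% of non-responders and 19.7% of responders go.
- ORR rises by 0.6 to 3.7 points.
- Median PFS rises by about 0.1 to 0.4 months (for example 3.66 to 3.97).
- Median OS falls by about 0.2 to 0.9 months if the later agent has no effect (for example 12.54 to 11.63). It falls by up to about 2.6 months if that agent halves the hazard (14.17 to 11.61).

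OS was timed here from the index line. That matches Table 2 only where the index line is also the first metastatic line.

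**The case against.** The strongest reply is that the wording is ambiguous and not plainly wrong. The eCRF screener text is not in the documents, and a provider may well take the criterion to mean prior or concurrent use. That stands as far as it goes: how the rule would be applied is unknown. It does not remove the problem, because section 9.2 expects about 20 or more providers and they could apply different rules with nothing to reveal it.

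A reader might go further and infer that the rule inflates ORR and favours afatinib. The documents do not support that. They give no rate of later TKI/ErbB use, overall or by response. Responders who later progress or stop for intolerance can also switch, and non-responders who die before switching stay in. Equal removal gives no ORR bias and reversed removal lowers it. The probable direction for OS is against the index drug. The criterion also applies to both cohorts.

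A reader might also infer that later therapy cannot touch PFS. Under Table 2 it can. A patient who stops for a reason other than progression and then dies counts as an event only if no other therapy came in between.

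Two points of context are fair. The study is descriptive, with no hypothesis and no between-cohort test. The plausible ORR shift is also smaller than the 10.7-point half-width. But it is systematic: the confidence interval does not reflect it, and adding patients does not shrink it. Section 9.9 admits patient selection bias in general terms, without naming this source.

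**Conclusion.** The point holds in this form: the exclusion lacks a time reference, its literal reading makes eligibility depend on post-index treatment, and different providers may read it differently. This is a source of selection bias that the plan neither prevents nor measures.

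The ORR and PFS bias is probably upward, because non-responders progress sooner and have more follow-up time in which to switch; that is a judgement and not a documented fact. The OS bias is probably downward. The size cannot be determined from the documents. The ORR range of 27.3% to 36.8% around a true 30%, and the simulated shifts, rest entirely on assumed inputs. A claim of certain inflation, or of bias in favour of afatinib overall, goes beyond the evidence. The change is still worth making before data collection, since it is cheap and the bias could not be reconstructed afterwards from the patients retained.

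**What to change.** Limit the exclusion to TKI/ErbB-directed therapy other than afatinib received before or together with the index therapy. Make the change in the Abstract, in section 9.2.1 and in the eCRF screener. Keep patients who receive such an agent after the index line and record it as subsequent therapy. Report, by cohort, the number excluded under the criterion.

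The cost is one phrase in two places, a screener edit and one count per cohort. Treatment sequence is already collected, so no new clinical data are needed for the patients retained. The downside is that OS will include the effect of later TKI/ErbB agents, as it already does for other later drugs. An OS analysis censored at the start of later therapy could be added only as a sensitivity analysis, labelled as subject to informative censoring, because switching tends to follow progression. The change does not alter the second cohort's own condition of no afatinib up to data collection, which should be named among the limitations.
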